6 INTERIM ANALYSES

Not applicable.

7 CHANGES IN THE PLANNED ANALYSES

Final analyses will be focused on the analyses planned in this document based on Phase 1b data due to the early termination of this study.

8 DEFINITIONS AND CONVENTIONS FOR DATA HANDLING

8.1 Data Report

Data reporting for both safety and efficacy analyses will use Safety Analysis Set, data reporting for PK analyses will use PK Analysis Set, and the DLT reporting will use DLT Evaluable Set. All the data reporting (tables, listings, figures) will be performed by dosing level. All descriptive statistics for continuous variables will be reported in mean, standard deviation (SD), median, Q1, Q3, minimum and maximum. Unless otherwise specified, all categorical variables will be summarized and reported in number (percentage) of subjects. The data summarized will be listed as well. Some data will only be listed if listing is enough for data reporting.

8.2 Baseline

Baseline is defined as the non-missing value most recently collected prior to the first dose of any study drugs.

8.3 Study Day

Study Day is defined as days from the first dosing date of any study drugs (i.e., PEGPH20 and Eribulin), in detail as

- For a date on or after the first dosing date, Study Day= event date first dosing date of any study drugs+1,
- For a date prior to the first dosing date, Study Day= event date first dosing date of any study drugs.

8.4 Day to Month to Year

1 month = 30.4375 days; 1 year = 365.25 days.

8.5 Censoring Rule

Table 2 shows the primary censoring rules for the derivation of PFS based upon investigator's tumor assessment and the Food and Drug Administration (FDA) "Guidance for Industry Clinical Trial Endpoints for the Approval of Cancer Drugs and Biologics (2007)".

No.	Situation	Date of Progression or Censoring	Outcome
1	No baseline tumor assessments	Date of the first dose	Censored
2	Progression documented between scheduled visits	Date of first radiologic PD assessment	Progressed
3	No progression at the time of data cut-off or withdrawal from study	Date of last adequate radiologic assessment prior to or on date of data cut-off or withdrawal from study	Censored
4	New anti-cancer treatment started	Date of last adequate radiologic assessment prior to or on date of new anti-cancer treatment	Censored
5	Death before first PD assessment	Date of death	Progressed
6	Death between adequate assessment visits*	Date of death	Progressed
7	Death or progression after two or more missed visit**	Date of last adequate radiologic assessment before missed tumor assessments	Censored
2	No post-baseline tumor assessments but known to be alive	Date of the first dose	Censored

 Table 2Censoring Rules for Analysis of Progression-Free Survival

CR = complete response, PD = progressive disease, PR = partial response, SD = stable disease,

* Adequate tumor assessment is a radiologic assessment of CR, PR, SD, non-CR/non-PD or PD as determined by investigators.

** More than two missed visits is defined if the duration between the last tumor assessment and death or PD is longer than 84 days (12 weeks) for subjects on the every 6 week scanning schedule during treatment /follow up phase in this study:

The priority of the censoring rules is as follows:

- 1. If the subject had PD or death, the following sequence will be applied:
 - If a subject did not have baseline tumor assessment (No. 1), the subject will be censored on date of the first dose. However, if the subject died or had clinical progression within 84 days (12 weeks) after the first dose and did not receive new anti-cancer treatment, the date of death or clinical progression will be the PFS event date (not censored).
 - If a subject had new anti-cancer treatment before PD or death (No. 4), the subject will be censored on the date of the last tumor assessment prior to or on the date of new anti-cancer treatment.
 - If a subject missed two assessments before PD or death (No. 7), the subject will be censored on the date of the last tumor assessment before PD or death. Note that if a subject is censored by both this criterion and the anti-cancer treatment criteria, the earliest censoring date will be used.
 - Otherwise, if a subject had an event (No. 2, No. 5 or No. 6), the earliest event date will be used.

2. If a subject did not have PD or death, the censoring date will be the earliest censoring date if the subject met multiple censoring criteria (No. 1, No. 3, No. 4, or No. 7).

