
assessments performed by the investigator. The secondary endpoint OS will be assessed throughout the study. All scans for tumor assessments performed during the study should be archived in accordance with the standard local practice. The scans must be submitted to a central core laboratory selected by the sponsor for potential central review.
 
Tumor assessments (CT chest and CT/MRI of abdomen, pelvis, and other areas of known disease at Screening plus any areas of newly suspected disease) should be performed at Screening (within 21 days prior to first dose of study drugs) and every 6 weeks ±1 week from the date of first dose of study drug, or sooner if clinically indicated, until documentation of disease progression. Skin lesions will not be included as target lesions, but may only be considered as non-target lesions.
 
A brain scan (CT with contrast or MRI pre- and post-gadolinium) must be performed at Screening (within 21 days prior to first dose of study drugs), to assess potential CNS disease and/or metastases. For the duration of the study (ie, post-Baseline), CT/MRI of the brain will be performed if clinically indicated, and within a target of 1 week after a subject achieves a complete response (CR). For subjects with a history of treated brain metastases, brain scans will be performed at tumor assessment time points, if clinically indicated.
 
A bone scan (^{99m}-technetium polyphosphonate scintigraphy, whole body bone MRI, or ¹⁸F-NaF-positron emission tomography [PET]) to assess bone metastases should be performed within 6 weeks prior to first dose of study drugs (historical scans are acceptable) and then every 24 weeks ±1 week after the date of first dose of study drugs, or sooner if clinically indicated.
	
assessments performed by the investigator. The secondary endpoint OS will be assessed throughout the study. All scans for tumor assessments performed during the study should be archived in accordance with the standard local practice. The scans must be submitted to a central core laboratory selected by the sponsor for potential central review.
 
Tumor assessments (CT chest and CT/MRI of abdomen, pelvis, and other areas of known disease at Screening plus any areas of newly suspected disease) should be performed at Screening (within 21 days prior to first dose of study drugs) and every 6 weeks ±1 week from the date of first dose of study drug (Phase 1b) or randomization (Phase 2), or sooner if clinically indicated, until documentation of disease progression. Skin lesions will not be included as target lesions, but may only be considered as non-target lesions.
 
A brain scan (CT with contrast or MRI pre- and post-gadolinium) must be performed at Screening (within 21 days prior to first dose of study drugs [Phase 1b] or randomization [Phase 2]), to assess potential CNS disease and/or metastases. For the duration of the study (ie, post-Baseline), CT/MRI of the brain will be performed if clinically indicated, and within a target of 1 week after a subject achieves a complete response (CR). For subjects with a history of treated brain metastases, brain scans will be performed at all tumor assessment time points, if clinically indicated.
 
A bone scan (^{99m}-technetium based polyphosphonate scintigraphy, whole body bone MRI, or ¹⁸F-NaF-positron emission tomography [PET]) to assess bone metastases should be performed within 6 weeks prior to first dose of study drugs (Phase 1b) or randomization (Phase 2) (historical scans are acceptable) and then every 24 weeks ±1 week after the date of first dose of study drugs (Phase 1b) or randomization (Phase 2), or sooner if clinically indicated.

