5 STATISTICAL METHODS

5.1 Study Endpoints

In this study, all the primary, secondary, and exploratory endpoints on tumor related measurement/definition would be from the investigator assessment per RECIST 1.1.

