5.1.2 Secondary Endpoints (Phase 2)

- Progression-Free Survival (PFS) defined as the time from date of randomization to date of first documentation of disease progression or death, whichever occurred first
- Overall Survival (OS) defined as the time from the date of randomization until date of death from any cause

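### The PFS rules in SAP 8.5 recognise only radiologic progression, which is narrower than the SAP's own RECIST endpoint, and they count clinical progression only when the baseline tumor assessment is missing

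*SAP*

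**What the plan says.** SAP 5.1 states that all tumor endpoints "would be from the investigator assessment per RECIST 1.1". SAP 5.1.2 ends PFS at the "date of first documentation of disease progression or death, whichever occurred first". SAP 5.4 carries this endpoint to Phase 1b, starting the clock at first dose. Neither section limits progression to imaging.

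SAP 8.5 introduces Table 2 as the "primary censoring rules for the derivation of PFS based upon investigator's tumor assessment". Row 2, for progression found between scheduled visits, gives the event date as "Date of first radiologic PD assessment". Footnote * reads: "Adequate tumor assessment is a radiologic assessment of CR, PR, SD, non-CR/non-PD or PD as determined by investigators". Rows 3, 4 and 7 censor at the last adequate radiologic assessment. The last row censors a living subject with no post-baseline tumor assessment at first dose.

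The priority list below the table mentions clinical progression once. A subject with no baseline assessment is censored at first dose, but has an event "if the subject died or had clinical progression within 84 days (12 weeks) after the first dose and did not receive new anti-cancer treatment". For everyone else the event rows are No. 2, No. 5 and No. 6, that is, row 2 progression or death.

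The protocol's efficacy assessments text (Section 9.5.1.5, as amended) says: "Skin lesions will not be included as target lesions, but may only be considered as non-target lesions".

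**The concern.** The derivation rules should implement the endpoint, and here they are worded more narrowly than it. Skin and chest-wall disease can progress, or appear, on examination without a scan. An investigator may record this as RECIST 1.1 progression through the non-target or new-lesion route, yet Table 2 offers no row that dates it. SAP 5.4 derives best overall response per RECIST 1.1 and lists non-target assessments, so the same finding could be progression for response and a censored observation for PFS.

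The treatment of clinical progression is also uneven. Whether a baseline assessment is missing should not decide whether a later clinical progression counts.

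Subjects who leave follow-up because of clinical or skin progression are plausibly at higher risk than those who remain. Censoring them would be informative and would lengthen the reported PFS quartiles and raise the 3-, 6- and 12-month rates. Two programmers could also derive different PFS dates from the same text.

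**Working it through.** The plan gives no figure on this point to reproduce. The check compares the texts and then illustrates the size.

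**1. Literal application of SAP 8.5.** Scans are every 6 weeks. The 84-day limit is 2 × 6 × 7 = 84 days, which is consistent. Week 4 is 28 days, inside the limit.

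| Living subject | Rule | PFS result |
|---|---|---|
| Stable at week-6 scan; investigator RECIST progression in a skin lesion before week 12; then new treatment | Row 4 | Censored at week 6 |
| Same, but no new treatment; withdraws without another scan | Row 3 | Censored at week 6 |
| No baseline assessment; clinical progression at week 4; no new treatment | Exception in priority list | Event at week 4 |
| Baseline scan; clinical progression at week 4; no later tumor assessment; no new treatment | Last row | Censored at first dose |
| Either of the two preceding subjects, but starting new treatment | Exception not met | Censored |

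Under SAP 5.1 and 5.1.2 the first two subjects have an event on the date the skin progression was documented. The third and fourth differ only in the baseline assessment and get opposite outcomes. The fifth line shows the limit of this asymmetry: once new treatment starts, neither group has an event.

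**2. Table against priority list.** Row 1 shows only censoring for a missing baseline. The priority list makes an exception for death or clinical progression within 84 days, which row 1 does not show.

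**3. Size, by simple arithmetic.** Assume 18 subjects at the RP2D (the planned number), 6 with radiologic progression by 3 months, and no other early censoring.
- Two further subjects progress early without a scan. Censored near time 0: 10/16 = 62.5%. Counted as events: 10/18 = 55.6%. Difference 6.9 points.
- One such subject: 11/17 = 64.7% against 11/18 = 61.1%. Difference 3.6 points.
- For scale, the approximate 95% half-width around 10/16 is 1.96 × √(0.625 × 0.375/16) = 0.237, about 24 points.

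**4. Size, by simulation.** Neither the share f of progressions documented without imaging nor the Phase 1b median PFS is in the documents. I assume f = 5% to 20% and medians of 4 to 8 months, with exponential times, scans every 42 days, no other censoring and 1,500 runs per cell. Non-imaging progressions are either counted on their date or censored at the preceding scan. Mean 6-month Kaplan-Meier rate, n = 30:

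| Median | f = 5% | f = 10% | f = 20% |
|---|---|---|---|
| 4 months | 0.381 → 0.399 | 0.382 → 0.419 | 0.378 → 0.458 |
| 6 months | 0.526 → 0.544 | 0.524 → 0.559 | 0.522 → 0.595 |
| 8 months | 0.620 → 0.635 | 0.617 → 0.648 | 0.615 → 0.679 |

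The rise runs from 0.015 (0.635 − 0.620) to 0.080 (0.458 − 0.378). Results for n = 18 are nearly the same. In large samples, censoring a fraction f of exponential events multiplies the median by about 1/(1 − f): 1.05, 1.11 and 1.25.

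**The case against.** The strongest reply is that *radiologic* is loose wording rather than a restriction. Table 2 is expressly built on the investigator's tumor assessment, the priority list branches on progression or death without the word radiologic, and row 2 is a dating rule for one situation. The protocol's RECIST appendix names the chest x-ray rule as its only departure from RECIST 1.1. On that reading a skin progression recorded by the investigator is progression, and row 4 does not apply because new treatment did not come before it. This much stands: a reader might infer that the SAP censors real progressions, but no text says so. That follows only if row 2 and footnote * are applied word for word.

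It also stands that leaving symptomatic deterioration without objective assessment out of a RECIST-based PFS is a legitimate choice. The no-baseline branch should be nearly empty because measurable disease is required at entry. Earlier scans are allowed when clinically indicated, and imaging is to continue after treatment stops without documented progression, so the week-4 subject is an edge case. Deaths generally remain events, subject to the new-treatment and missed-visit rules.

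The reply does not remove the mismatch. The SAP never says how progression seen only on examination is dated. Clinical progression is named separately from PD, so it cannot simply be read into row 2 for subjects with a baseline scan.

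**Conclusion.** The point holds as a mismatch in wording and an uneven rule. Table 2 row 2 and footnote * are narrower than the SAP's endpoint and do not fit skin lesions followed as non-target disease. As written, they allow a RECIST progression seen on examination to be censored under row 3 or 4. Clinical progression is an event only without a baseline assessment, and that exception disagrees with row 1.

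The direction is toward longer PFS. The size is unknown and probably small. The 0.015 to 0.08 rise in the 6-month rate rests entirely on the assumed shares and medians, and on every non-imaging progression being censored. The 7-point example rests on an assumed two cases in 18. Sampling error is much larger than either. Phase 1b PFS is descriptive, in at most 30 planned subjects reported by dose level, and the primary endpoint is the RP2D, so no decision rule is affected. The documents do not show that any subject's progression was in fact censored.

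**What to change.** 1. In Table 2 row 2 and footnote *, replace the radiologic wording with *investigator tumor assessment per RECIST 1.1, including clinically assessed non-target and new skin lesions*, and make the matching change in rows 3, 4 and 7. State that an adequate assessment must yield an investigator overall response in one of the categories the footnote lists, so that an isolated skin examination without progression does not move a censoring date.
2. Apply one clinical-progression rule to all subjects, whatever their baseline assessment. For the primary analysis, delete clinical progression from the no-baseline exception and show the remaining death exception in row 1. This turns any such event in a subject without a baseline assessment into a censoring, so step 3 is needed alongside it.
3. Add one sensitivity Kaplan-Meier analysis in which clinical progression without a scan is an event on its date for every subject, provided the CRF records that date. The CRF is not among the documents, so this needs checking.

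The cost is a change of SAP wording, which the SAP foresees being settled before database lock, plus one extra Kaplan-Meier run. The reported PFS may be slightly less favourable.

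### PFS censoring rule No. 7 detects missed scans by an 84-day gap that ignores the ±1 week scan window, so progression after one missed scan can be censored

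*SAP*

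**What the plan says.** SAP sections 3.2.3 and 3.2.4 schedule tumor assessments every 6 weeks ±1 week. Section 3.2.4 counts them from first dose and allows an earlier scan when clinically indicated.

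SAP section 8.5 describes rule No. 7 in three places:

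- Table 2, row 7, gives the situation as "Death or progression after two or more missed visit" and the censoring date as "Date of last adequate radiologic assessment before missed tumor assessments".
- The footnote to that row begins "More than two missed visits is defined" and sets the test: "if the duration between the last tumor assessment and death or PD is longer than 84 days (12 weeks".
- The priority list says "If a subject missed two assessments before PD or death (No. 7" and then "the subject will be censored on the date of the last tumor assessment before PD or death".

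Row 5, "Death before first PD assessment", is an event on the date of death with no time limit. For subjects with progression or death, the priority list is an ordered sequence that applies No. 7 before No. 5. Priority item 2, for subjects with neither, also names No. 7.

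SAP section 5.4 plans Kaplan-Meier quartiles of PFS and rates at 3, 6 and 12 months with 95% confidence intervals, timed from first dose. Section 8.1 reports all data by dosing level.

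**The concern.** Row 7 states a criterion in missed visits, and the footnote turns it into days. The conversion works only if every scan falls on its nominal day. Under the SAP's own ±1 week window, a subject who missed one scan can pass the test for two. A progression that row 7 would keep as an event is then removed and the subject is censored back to the last scan. This raises the Kaplan-Meier estimate from the progression date onward. Between the censoring date and the progression date the estimate can be slightly lower, because one subject fewer is at risk.

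The texts also disagree on the count (two or more, more than two, two) and on the censoring date (last adequate assessment before the missed ones, or last tumor assessment before the event). The start of the gap is not stated for a subject with no post-baseline scan. Two programmers could follow section 8.5 and derive different PFS data.

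**Working it through.** **Inputs.** Interval 42 days and window ±7 days, anchored on first dose (SAP 3.2.4); cut-off more than 84 days (SAP 8.5 footnote); screening period of 21 days (SAP 3.2.3).

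**The plan's figure.** 2 × 42 = 84 days, which is two intervals with a window of zero.

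**Last assessment is an on-study scan.** Let the last scan be a days off its nominal day and the progression scan b days off, each from −7 to +7. With m missed scans in between, gap = 42 × (m + 1) + b − a.

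| Missed scans | Gap (days) | Over 84 |
|---|---|---|
| 0 | 28–56 | never |
| 1 | 70–98 | when b > a |
| 2 | 112–140 | always |

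These ranges are for progression found at scheduled, in-window scans; unscheduled scans are not modelled.

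Example: scan on day 42, week-12 scan missed, progression on day 127 (week 18 plus 1 day). The gap is 85 days with one scan missed, and the subject is censored at day 42. At the extreme, a scan on day 35 and progression on day 133 give 98 days.

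**Share of one-missed cases over 84 days.** Assume independent uniform whole-day offsets on ±w. Then P(b > a) = w/(2w + 1): 0 for w = 0, 3/9 = 33% for w = 1, 21/49 = 43% for w = 3 and 105/225 = 47% for w = 7. For other timing patterns the share can lie anywhere from 0% to 100%.

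**Deaths.** After a scan on day 42 + a, the second missed window closes on day 126 + 7 = 133, which is 91 − a days later (84 to 98). With a = −7, a death 85 to 97 days after the scan is censored while the second window is still open.

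**Last assessment is the baseline scan.** Taken s = 0 to 21 days before first dose, with the week-6 scan missed and progression at week 12, the gap counted from that scan is 84 + b + s, or 77 to 112 days. Counted from first dose it is 84 + b, or 77 to 91 days. The SAP does not say which count applies. The No. 1 exception, by contrast, names its origin: "if the subject died or had clinical progression within 84 days (12 weeks) after the first dose".

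**Adequate scan or any scan.** Take an adequate scan on day 42, a non-evaluable scan on day 84, the day-126 scan missed and progression on day 168. From the last adequate scan the gap is 126 days and the subject is censored. From the last scan of any kind it is 84 days and the progression is an event.

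**Size in a small group.** Planned sizes are 6 per run-in cohort and 18 at the RP2D (SAP 3.2.1). Assume n subjects, m events by six months, no other censoring, and one progression on day 127 censored at day 42 after k earlier events. The six-month rate moves from (n − m)/n to ((n − k)/n) × (n − m)/(n − k − 1).

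- n = 6, m = 3: 0.500 becomes 3/5 = 0.600 (k = 0) up to 4/6 = 0.667 (k = 2).
- n = 18, m = 9: 0.500 becomes 9/17 = 0.529 (k = 0) up to 10/18 = 0.556 (k = 8).

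With the six-month rate assumed between 33% and 67%, the rise is 7 to 17 percentage points for n = 6 and 2 to 6 for n = 18. In the other direction, with n = 6, k = 0 and one other event after day 42 and before three months, the three-month rate falls from 5/6 = 0.833 to 4/5 = 0.800.

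**The case against.** **84 days is a defensible trade-off.** If the last scan is on day 49, the second missed window closes on day 133, which is 84 days later. More than 84 days is therefore the largest single cut-off that catches every progression or death after two closed windows following an on-study scan. This stands. It also shows why the obvious repair, 2 × 49 = 98 days, is not a correction: after a scan on day 49, deaths or unscheduled progressions on days 134 to 147 would stay events although two windows had closed. Gaps of 85 to 98 days can arise either way, so any single cut-off misclassifies one side. Nor is 98 days a ceiling if the gap is counted from the baseline scan.

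**The footnote is itself the definition, and it can be programmed.** For a subject with an adequate on-study scan, that is so. But the footnote presents the number as a measure of missed visits, and under the SAP's own schedule it does not measure that. Derivation rules also go into a separate dataset specification (SAP section 9), which is not among the documents and might add a window. It should not have to override an explicit number in the SAP.

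**Two stronger readings are tempting.** A reader might infer that the SAP leaves open whether row 5 or No. 7 governs a late death with no post-baseline scan. It does not: the priority sequence ranks No. 7 first. What is missing is the start of the gap, and row 5 carries no limit to match that ranking. A reader might also infer that nearly half of progressions after a missed scan are lost. That figure holds only given exactly one missed scan, progression at the next scheduled scan, and the assumed offsets.

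**Conclusion.** The point holds and is minor. The 84-day test can censor progression 85 to 98 days after an on-study scan when only one scan was missed, and a death at 85 to 97 days while the second window is open. The ranges follow from the SAP's schedule alone. How often this happens cannot be derived from the documents, and the shifts of 2 to 17 percentage points rest on the assumption that one progression is reclassified. The study ended early and the SAP covers Phase 1b only. PFS there is descriptive, by dose level, under an exploratory objective, and the data are listed. A reader might infer a threat to the trial's conclusions, but no test, sample size or dose decision depends on this rule.

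**What to change.** - Define No. 7 as two or more consecutive scheduled windows (week 6k ±1 from first dose) that closed with no adequate assessment before the progression or death. Do not simply substitute 98 for 84 days.
- Use the same count (two or more) and the same censoring date (last adequate assessment before the missed ones) in row 7, the footnote and the priority list.
- With no post-baseline scan, count from first dose and never censor before it. Table 2 already censors living subjects without a post-baseline scan at first dose.
- Reconcile row 5 with the priority sequence, so that it is explicit when a late death is an event.
- Remove No. 7 from priority item 2, since row 7 requires a progression or death.
- Say whether the 84-day limit in the No. 1 exception is kept on purpose.

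The cost is wording in the SAP and the dataset specification before database lock, plus deriving each subject's scheduled windows. No additional data need to be collected.
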